#### 3. INTRODUCTION

# 3.1 Background Information

HCP are believed to be at increased risk of influenza virus infection due to a higher rate of exposure compared with the general population. Close contact with patients may further result in transmission to patients. Vaccination is the most effective method of preventing influenza, and HCP were identified by the World Health Organization as a priority population to target for influenza vaccination. However, there is limited information on the effectiveness of influenza vaccines among HCP. Reports of reduced influenza vaccine effectiveness among persons with a history of frequent influenza vaccination in some studies and seasons also make it especially important to examine influenza vaccine effects among HCP. Recent studies of influenza vaccine immunogenicity among HCP have demonstrated that repeated vaccination can blunt the antibody response to hemagglutinin (HA) and neuraminidase (NA).

Influenza vaccine efficacy varies annually depending on the match between vaccine strains and circulating strains, and by influenza virus type and subtype.  Reduced influenza vaccine effectiveness has been observed for A/H3N2 viruses over the past several influenza seasons in the United States,  and in Israel,  and has been associated with mutations that can occur during the production of inactivated influenza vaccines (IIV). Specifically, circulating influenza viruses are adapted for growth in embryonated chicken eggs, and then grown in large scale to produce the vaccine.  Both the adaptation process and serial passage of influenza viruses in chicken eggs can result in the development of mutations that have been associated with diminished vaccine effectiveness against both A/H3N2 and A/H1N1 viruses. 

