### 4. STUDY OBJECTIVES

## 4.1 Primary Objective

- Compare humoral immune responses to a single dose of RIV4 versus IIV4 at approximately 28 days after vaccination in the 2019-20 season among HCP ≥ 18 years old who were vaccinated in the 2018-19 season with IIV4 (defined as Group One) as measured by
  - hemagglutination inhibition (HI) titers for egg-grown influenza viruses A/H1N1,
     B/Yamagata, and B/Victoria, and egg-grown and cell-grown A/H3N2
  - o microneutralization (MN) titers for egg-grown and cell-grown A/H3N2 viruses

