# **6.2 Study Setting and Source Population**

This study will be conducted among HCP who were enrolled in SHIRI for at least one year. SHIRI was conducted during the 2016-2017, 2017-2018, and 2018-2019 influenza seasons at the following two hospitals:

Beilinson Hospital, Rabin Medical Center, Petah Tikva, Israel Soroka Medical Center, Beersheva, Israel

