### Inclusion criteria:

- 1. Aged ≥18
- 2. Are currently a member of Clalit Health Services
- 3. Consent to randomized receipt of influenza vaccination with either RIV4 or IIV4, or, if already vaccinated in the current year outside of the study, consent to receive a post-vaccination blood draw
- 4. HCP Group One participation criteria:
  - Participated in the SHIRI study and received influenza vaccination during the
     2018-19 influenza season
- 5. HCP Group Two participation criteria:
  - Participated in any year of the SHIRI study and had PCR-confirmed influenza virus infection during any of the three study years;
- 6. HCP Group One Supplemental criteria:
  - Participated in any year of the SHIRI study, not vaccinated in 2018-2019, but vaccinated in at least one study year;
  - Participated in the SHIRI study during all three years, regardless of vaccination status

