#### 6.3.4 Randomization

Using the list of HCP consented to participate in the study, HCP will be randomized 1:1 to receive one 0.5 mL intramuscular dose of Flublok® Quadrivalent or Vaxigrip Quadrivalent. Randomization lists will be generated by the epidemiologist and data analyst using block randomization to ensure equal sample size in each group.

Randomization will be conducted after enrollment is completed. Randomization will occur separately for participants in Group One and Group Two.

Randomization will not occur for enrolled participants who were vaccinated with Vaxigrip outside of the study.

# 6.4 Study visit 1

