#### 9. DATA ANALYSIS

# 9.1 Power and Sample Size Considerations

To guide enrollment goals, we estimated the sample size required to do a two-sided test with a significance level of 0.05 and a power of 80%. The Food and Drug Administration criteria for demonstrating non-inferiority between IIV and a new vaccine requires comparisons of both the GMR and the SCR. We based expected values for the SCRs and GMRs comparing RIV3 and IIV3 on previously published estimates from prior vaccine immunogenicity trials. We assume that the SCR for IIV4 is  $\geq$ 40% and  $\geq$ 55% for RIV4, based on a clinical trial among adults <65 years demonstrating the SCR for IIV4 to range from 35% to 60% and RIV4 to range from 54%

to 63% against influenza A subtypes (seroconversion rates reported against influenza B viruses reflected trivalent vaccine formulations and were not included).  $^{23,32}$  We intend to have the power to show a 30% relative increase in SCR in the RIV arm compared to the IIV arm. Using the same assumptions and sample size would also provide adequate statistical power to detect a difference in post-vaccination GMT of  $\geq$ 2 fold between study arms if post-vaccination GMT value is  $\geq$ 20 for IIV4 and  $\geq$ 40 for RIV4. **Table 2** provides estimated sample sizes required for varying SCR and differences in SCR between study arms.

Based on prior experience enrolling participants at the two study sites, we will assume that 5% of participants will drop out before study visit 2.

Table 2. Sample size calculations to detect specified differences in SCR between RIV4 and IIV4 at approximately 28 days post-influenza vaccination

SCR at 28 days post- vaccination in IIV arm	Relative increase (%) in SCR in RIV arm compared to IIV arm at 28 days post-vaccination	IV arm Total enrollment for both study arms	
30%	10%	7526	
30%	20%	1926	
30%	30%	874	
40%	10%	4778	
40%	20%	1208	
40%	30%	540	
50%	10%	3130	
50%	20%	776	
50%	30%	340	
60%	10%	2032	
60%	20%	488	
60%	30%	206	

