## Secondary Objectives

To compare immune responses among Group Two participants with a history of PCR-confirmed influenza infection a linear regression predicting log transformed titer will be created with independent variables for year of influenza infection, type of influenza virus detected, study arm, and potential confounders. We assume confounding will be eliminated by randomization and that models will not be adjusted unless differences in study arms are found during univariate analysis.

To assess prior vaccination status among Group One participants (number of influenza vaccinations received during the preceding 10 years) as an effect modifier of differences in GMTs, a linear regression predicting log transformed titer will be created with independent variables for vaccine history, study arm, and potential confounders, and an interaction term between study arm and vaccine history.

All primary analyses will be conducted as intention-to-treat. All tests will be 2-tailed with a level of significance of .05.

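### The rule for adjusting the secondary models checks only balance between vaccine arms, which leaves the comparison by infection history open to confounding it cannot detect

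*Combined protocol and SAP*

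**What the plan says.** Section 9.2, Secondary Objectives, describes a linear regression of log titre among Group Two participants. Its terms are infection year, virus type, study arm and potential confounders. It then states: "We assume confounding will be eliminated by randomization and that models will not be adjusted unless differences in study arms are found during univariate analysis." The next paragraph, on vaccination history in Group One, lists history, arm, potential confounders and an arm-by-history interaction, and does not repeat the rule. Neither paragraph names a confounder.

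The other relevant statements are:

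- **What is randomised (6.3.4).** "HCP will be randomized 1:1 to receive one 0.5 mL intramuscular dose", separately within Group One and Group Two. HCP who had Vaxigrip outside the study are not randomised, although section 6.1 counts them in the Vaxigrip arm.
- **The contrast (4.2).** Responses to RIV4 and IIV4 in HCP with PCR-confirmed infection in any of three seasons, set against those without.
- **Group One (4.1).** HCP "vaccinated in the 2018-19 season with IIV4 (defined as Group One". Section 6.3.1 repeats the vaccination requirement and does not exclude infected HCP.
- **Group Two (6.3.1).** "Participated in any year of the SHIRI study and had PCR-confirmed influenza virus infection during any of the three study years". No vaccination requirement is given.
- **Group One Supplemental (6.3.1, 6.3.2).** May include HCP not vaccinated in 2018-19, and is used only if Group One recruitment falls short.
- **Source population (6.2).** "This study will be conducted among HCP who were enrolled in SHIRI for at least one year".
- **Background (3.1).** Studies in HCP show that "repeated vaccination can blunt the antibody response to hemagglutinin (HA) and neuraminidase (NA".

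**The concern.** Randomisation makes the two vaccine arms comparable. It does nothing to make infected and uninfected HCP comparable. The only trigger for adjustment is a difference between arms, and that check carries no information about the infection-history contrast.

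Eligibility supplies a concrete route to imbalance. A comparator drawn from Group One is vaccinated in 2018-19 by definition, while Group Two may contain any share of vaccinated HCP. The plan itself regards prior vaccination as related to response. A higher response in Group Two could therefore reflect less recent vaccination rather than past infection, and balanced arms would pass the check and leave that in place.

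The rule also pulls against its own paragraph: potential confounders are model terms in one sentence and excluded by default in the next. Two analysts could follow the text and fit different models.

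**Working it through.** **1. The plan's own figure.** The documents give no figure for the secondary objectives. The design figure is Table 2's total of 540, for an SCR of 40% against 52%, using a "two-sided test with a significance level of 0.05 and a power of 80"%. With pooled variance and a mean proportion of 0.46:

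n per arm = [1.960 × √(2 × 0.46 × 0.54) + 0.842 × √(0.40 × 0.60 + 0.52 × 0.48)]² / 0.12² = 269.6, so 270 per arm and 540 in total.

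This reproduces, and nothing below changes it.

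**2. Bias in an unadjusted infected-versus-uninfected comparison.** Let v be the share of infected HCP vaccinated in 2018-19, w the share of the uninfected comparator, and e the log2 reduction in response from that vaccination. With no true infection effect:

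bias = (w − v) × e log2; spurious ratio = 2^bias.

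The documents give none of v, w or e. Assumed: e = 0.5 or 1.0; v = 30%, 50% or 70%; w = 100% (Group One only) or 80% (some Supplemental HCP).

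| w | e | v = 30% | v = 50% | v = 70% |
|---|---|---|---|---|
| 100% | 1.0 | 2^0.70 = 1.62 | 2^0.50 = 1.41 | 2^0.30 = 1.23 |
| 100% | 0.5 | 2^0.35 = 1.27 | 2^0.25 = 1.19 | 2^0.15 = 1.11 |
| 80% | 1.0 | 2^0.50 = 1.41 | 2^0.30 = 1.23 | 2^0.10 = 1.07 |
| 80% | 0.5 | 2^0.25 = 1.19 | 2^0.15 = 1.11 | 2^0.05 = 1.04 |

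If v = w the bias is nil. If v exceeds w it reverses sign: v = 100%, w = 80%, e = 1.0 gives 2^(−0.20) = 0.87.

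**3. False-positive rate.** Simulation, 1,500 runs per setting: 110 infected and 440 uninfected (the 6.3.2 targets), arms randomised 1:1 within each group, residual SD 2 log2 (assumed).

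| w | e | v = 30% | v = 50% | v = 70% |
|---|---|---|---|---|
| 100% | 1.0 | 90% | 64% | 29% |
| 100% | 0.5 | 36% | 21% | 12% |
| 80% | 1.0 | 63% | 28% | 8% |
| 80% | 0.5 | 22% | 13% | 7% |

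A hand check agrees: the standard error is 2 × √(1/110 + 1/440) = 0.213, and 0.70/0.213 = 3.28, which implies rejection in about 91% of trials. With 2018-19 vaccination in the model the bias is about 0 and rejection is 4% to 7%.

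**4. Would the rule detect it?** In these runs, a test for an arm difference in 2018-19 vaccination was significant in about 0% to 5% of trials. Adjustment would almost never be triggered.

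**5. If the objective is read as an arm-by-infection interaction.** Without modification of the arm effect by vaccination, the interaction is unbiased (about 4% to 5% rejection). With an assumed 0.5 log2 modification and w = 100%, its bias is (v − w) × 0.5 = −0.35, −0.25 and −0.15 at v = 30%, 50% and 70%, with rejection of 13%, 9% and 7%. The RIV4 versus IIV4 estimate within Group Two is unbiased: 0.97 to 1.01 against a true 1.0 in the runs without modification.

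**6. Vaccination history in Group One.** Take 440 × 0.95 = 418 after 5% dropout and SD 2. The history-by-arm term per SD of history has standard error 2 × 2/√418 = 0.196. If age correlates r with history and modifies the arm effect by b per SD, that term absorbs r × b. With r = 0.3 to 0.5 and b = 0.4 to 0.6 (all assumed), this is 0.12 to 0.30 log2, and simulated rejection is 9% to 34%. It is 9% to 35% with age as a main effect only, and about 5% with age-by-arm added. With b = 0.1 to 0.2 it is only about 5% to 8%.

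**The case against.** Several points on the other side stand.

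- A reader might infer that the analysis as written produces a confounded infected-versus-uninfected result. It does not, because the Group Two model is fitted among infected HCP and has no infected/uninfected term. That mismatch with section 4.2 is a separate matter. The point here is what happens when the objective in 4.2 is carried out under the stated rule.
- Section 4.2 can be read as asking whether the arm effect differs by infection history. That interaction is affected only if prior vaccination modifies the arm effect. Section 3.1 does cite sub-analyses with a greater response to Flublok than IIV in previously vaccinated people, so this is plausible but not established.
- A reader might infer that the rule also bars adjustment of the vaccination-history model. It is not stated in that paragraph, and that model lists potential confounders. A history-by-arm term validly describes heterogeneity; only attributing it to vaccination history needs control of age and the like. Nothing in the documents says that vaccination count rises with age or that age modifies the arm effect.
- A reader might treat Group One as the uninfected side. It is not defined so, Group Two members may have been vaccinated, and Supplemental HCP may not have been. The tie between infection and vaccination is partial.
- Sections 3.1 and 3.2 concern repeated vaccination, not one season's dose, and give no effect size.

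None of this rescues the rule, because arm balance still says nothing about a history that was not randomised.

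**Conclusion.** The concern holds in limited form. The no-adjustment rule is sound for RIV4 versus IIV4 among randomised participants and has no bearing on confounding of infection history. With 2018-19 vaccination required of Group One and not of Group Two, the infected-versus-uninfected comparison is open to confounding that the rule cannot detect, and the rule contradicts the covariates listed in its own model.

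Confidence in that logic is high; confidence in any particular size is not. The 1.11 to 1.62 range rests wholly on the assumed effect and shares with an all-vaccinated comparator. It shrinks with Supplemental HCP, vanishes with equal shares, and could reverse.

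The documents do not support saying that the secondary results will be biased, that the randomised arm contrast is compromised by this rule, or that Table 2 is wrong. Only secondary analyses are affected, so this is a change that should be made rather than a flaw in the primary design.

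**What to change.** In section 9.2:

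1. Limit the sentence on randomisation and its arm-difference trigger to RIV4 versus IIV4 among randomised participants.
2. For the infection-history analysis, adjust whatever the arm balance for 2018-19 vaccination (or prior vaccination count), age, site and chronic conditions.
3. For the Group One vaccination-history model, adjust for age, site and chronic conditions. Leave out 2018-19 vaccination: it is constant in Group One apart from Supplemental HCP, and is part of the 10-year count. Report the history-by-arm term also with age-by-arm included.
4. Describe both as observational contrasts within the trial.
5. State as a limitation that HCP were under SHIRI surveillance for unequal numbers of seasons, so some classed as uninfected were simply not observed. A season-count covariate cannot recover missed infections; a sensitivity analysis in HCP observed for all three seasons is more informative.

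Cost: SAP wording. Section 6.7 already provides for SHIRI linkage, demographics, chronic conditions and 10-year vaccination history. The price is a few degrees of freedom and a somewhat wider interval for the interaction. If every comparator was vaccinated, the adjusted infection contrast rests on the vaccinated part of Group Two. At v = 50% (55 HCP) and SD 2, its standard error rises from 0.213 to 2 × √(1/55 + 1/440) = 0.286. That wider interval reflects how much comparable information the design holds.

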# 4.2 Secondary Objectives

- Compare humoral immune responses to a single dose of RIV4 versus IIV4 at 28 days post-vaccination in the 2019-20 season among HCP with a history of PCR-confirmed influenza infection during any of the three study years (2016-17 through 2018-19) compared to those without PCR-confirmed influenza infection (defined as Group Two);
- Compare humoral immune responses at 28 days post-vaccination as stated in the primary objective but with secondary indicators of humoral immune response using MN titers for other virus subtypes/lineages, as appropriate;
- Examine whether the number of prior influenza vaccinations during the preceding 10 years, as documented by medical records, modifies humoral immune responses after a single dose of RIV4 or IIV4 at approximately 28 days after receipt of the 2019-20 vaccines as measured by
  - HI titers for influenza A/H1N1, influenza B/Yamagata, and influenza B/Victoria strains and
  - o MN titers for influenza A/H3N2 viruses

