# 4.3 Exploratory Objectives

- Examine whether any association between prior vaccination and immune response to 2019-20 vaccination is mediated by antibodies to the prior vaccine strains
- Gather information on any adverse events following vaccination
- Characterize humoral immune responses as measured by HI, MN titers, and other
  appropriate humoral immunity assays among subsets of enrollees of particular interest
  due to their age or demographic characteristics, health status, and/or occupational roles
  and responsibilities.

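### The prior-vaccination model leaves out day-0 titre: the planned interaction test is unbiased among randomised participants but loses precision, and an unadjusted history slope would mix antibody already present with response

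*Combined protocol and SAP*

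**What the plan says.** Section 4.2 sets the secondary objective: "Examine whether the number of prior influenza vaccinations during the preceding 10 years, as documented by medical records, modifies humoral immune responses" at about 28 days, measured by HI and MN titres. Section 3.1 gives the motivation, that "repeated vaccination can blunt the antibody response". Section 4.3 adds an exploratory question: whether "any association between prior vaccination and immune response to 2019-20 vaccination" is mediated by antibodies to earlier vaccine strains.

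Section 9.2 (Secondary Objectives) has one model for this. History is assessed "as an effect modifier of differences in GMTs". The model is described as follows: "a linear regression predicting log transformed titer will be created with independent variables for vaccine history, study arm, and potential confounders". The term that carries the test of modification is "an interaction term between study arm and vaccine history". No time point is given for the titre, and the confounders are not named.

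The nearest adjustment rule is in the Group Two paragraph just before it: "models will not be adjusted unless differences in study arms are found during univariate analysis". Fold rise (GMR) is one of the four parameters listed at the start of 9.2, but under the primary objective it is modelled only between vaccine groups, not by history. Sections 6.1 and 6.4.2 provide a day-0 blood draw for every randomised participant.

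**The concern.** Day-28 titre reflects both what a person had before the dose and what the dose added. Number of prior vaccinations is not randomised, and frequent vaccinees may start higher. The adjustment rule responds to differences between arms, so it would not bring day-0 titre in merely because that titre varies with history.

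Two things are at stake:

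- **Precision.** Variation in day-0 titre stays in the error term of the interaction test, although the samples to remove it are already planned.
- **Interpretation.** Blunting common to both vaccines cannot appear in the interaction. It can appear only in the history slope within each arm. If that slope is used to answer section 4.2 or 4.3, an unadjusted version can hide blunting or reverse its sign.

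**Working it through.** **1. The plan's own figures.** The documents give no sample size, power, slope or SD for this model. The nearest figure is Table 2, IIV4 SCR 40% with a 30% relative increase (40% against 52%). With pooled variance, two-sided 0.05 and 80% power, n per arm = [1.960·√(2·0.46·0.54) + 0.842·√(0.24 + 0.2496)]² / 0.12² = 269.6, so 270 per arm and 540 in total, as printed. It sizes the SCR comparison and does not bear on this model.

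**2. Inputs.**
- From the documents: Group One target 440 (6.3.2), 5% dropout (9.1), 1:1 allocation (6.3.4), two-sided 0.05 (9.2). 440 × 0.95 = 418, or 209 per arm if all are randomised.
- Assumed: prior doses uniform on 1 to 10, so variance (10² − 1)/12 = 8.25; log2 SDs 1.8 (day 0) and 1.4 (residual); coefficient ρ of day-28 on day-0 titre, 0.6 or 1.0.

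**3. Precision of the interaction.** SE = σ·√(2/(209 × 8.25)) = 0.0341·σ. Without day-0 titre, σ = √(ρ²·1.8² + 1.4²); with it, σ = 1.4.

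| Model | σ | SE | Power for 0.12 per dose |
|---|---|---|---|
| Unadjusted, ρ = 0.6 | √3.126 = 1.768 | 0.060 | about 52% |
| Unadjusted, ρ = 1.0 | √5.20 = 2.280 | 0.078 | about 34% |
| Day-0 adjusted | 1.4 | 0.048 | about 70% |

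With smaller assumed SDs (1.5 and 1.3, ρ = 1.0) the SE falls from 0.068 to 0.044, and power for 0.10 rises from 32% to about 60%. In 2,000 simulated trials per scenario with these smaller SDs, a true interaction of zero was estimated at about zero and rejected in 4% to 6% of runs, with or without adjustment. Omitting day-0 titre therefore does not bias this test among randomised participants.

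**4. The history slope within an arm.** Let b be the effect of one prior dose on day-0 log2 titre, and d its effect on day-28 titre at equal day-0 titre. Then:
- unadjusted day-28 slope = ρb + d
- fold-rise slope = (ρ − 1)b + d
- day-0-adjusted slope = d

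With ρ = 1.0 and d = −0.10 (simulation, SDs 1.5 and 1.3):

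| b (assumed) | Unadjusted slope | Significant |
|---|---|---|
| 0 | −0.10 | 55% |
| +0.05 | −0.05 | 19% |
| +0.10 | 0.00 | 5% |
| +0.15 | +0.05 | 17% |
| +0.20 | +0.10 | 57% |

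The fold-rise and day-0-adjusted slopes stay at about −0.10 throughout, with 85% to 89% power.

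**5. Fold rise is not a neutral yardstick.** With ρ = 0.6, b = +0.20 and d = 0, the fold-rise slope is (0.6 − 1) × 0.20 = −0.08. With SDs 1.8 and 1.4 it is significant in 56% of runs, although history has no effect at equal day-0 titre. The adjusted slope is 0.00 (5%). Equally, at ρ = 0.6 and b = +0.20, a fold-rise slope of −0.10 is −0.08 from baseline and only −0.02 from history at equal baseline. If instead d = −0.10, the unadjusted slope is 0.6 × 0.20 − 0.10 = +0.02, so masking is still possible.

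**6. Participants vaccinated outside the study.** They join the IIV4 arm without randomisation (6.1, 6.3.4), and their baseline is the end-of-season SHIRI serum (6.4.2). If they are a share w of that arm and their day-0 slope differs by δ, the unadjusted interaction shifts by about −wδ when ρ = 1.0, given a similar spread of history. The documents do not give w or δ.

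**The case against.** The strongest reply is that the model has a different target. Its stated purpose is to test history as a modifier of the difference between arms, and the interaction does that without bias among randomised participants. No test of the within-arm slope is written into 9.2, and section 4.2 says response is measured by titres, not fold rise. This stands. A reader might infer that the planned test itself can hide or reverse blunting; the documents do not support that, because randomisation makes day-0 titre's expected relation to history the same in both arms.

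It is also fair that a day-28 outcome is inferred, that unnamed confounders do not exclude day-0 titre, and that GMR is listed for all HI and MN results. These leave the choice open rather than settle it.

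A reader might also infer that fold rise should decide whether blunting occurred. Step 5 shows why not: it can produce apparent blunting from higher baselines alone.

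Finally, a reader might infer that the unadjusted association is the wrong start for the mediation question in 4.3. If antibody already present is the mediator, the unadjusted slope is the total association and a legitimate start.

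What the reply does not remove is the loss of precision, or the ambiguity of the history slope. The wording of 4.2, that history "modifies humoral immune responses after a single dose of RIV4 or IIV4", can be read as asking for that slope, and 4.3 refers to an overall association.

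**Conclusion.** The point holds in two limited parts.

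- **Precision.** The interaction test gives up precision that planned samples could supply. The SE falls by about a fifth (0.060 to 0.048) at ρ = 0.6, or nearly two fifths (0.078 to 0.048) at ρ = 1.0. This rests on the assumed SDs, a uniform 1 to 10 doses, and 418 randomised participants.
- **Interpretation.** If the within-arm history slope is read as an answer to 4.2 or 4.3, the unadjusted slope carries the effect of history on day-0 titre. The size and sign of the distortion depend on a day-0 slope that the documents do not give: none at slope 0, full masking of −0.10 at +0.10, reversal at +0.20 (ρ = 1.0).

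The documents do not show that masking will occur, and the primary comparison is not affected.

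**What to change.** In the prior-vaccination paragraph of 9.2, for randomised participants:

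1. State that the outcome is the log2 titre at about day 28.
2. Add log2 day-0 titre as a covariate to the arm, history and arm-by-history model, and test the interaction from that model.
3. Report the history slope in each arm from the adjusted model, with the unadjusted day-28 slope and the log2 fold-rise slope beside it.
4. Say that blunting will not be judged on fold rise alone. Say also that day-0 titre may be a mediator (4.3), so the unadjusted slope remains the total association.

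The cost is a few lines of wording and one or two extra fits per antigen. No new data are needed. The downside is that three slopes must be presented and explained, because they answer different questions.

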# 3.3 Expected benefits from the proposed study

Influenza results in substantial morbidity and mortality, and annual vaccination remains the most effective method to prevent influenza and its complications. Through this study, we will gain a better understanding of whether RIV4 (Flublok® Quadrivalent) offers greater protection to HCP than the conventional egg-based IIV4 (Vaxigrip® Quadrivalent) as measured primarily by humoral immune responses to MDCK cell-grown vaccine strains.

In the United States, both vaccines are licensed for use in adults aged  $\geq 18$  years based on phase III trials demonstrating efficacy in comparison to placebo or non-inferiority to conventional egg-based influenza vaccines. Therefore, study participants may directly benefit from receipt of study vaccine by receiving protection against circulating influenza viruses during the 2019-20 influenza season. In Israel, only IIV4 is licensed for use in adults aged  $\geq 18$ .

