# 5. STUDY ENDPOINTS

# **5.1 Primary Endpoints**

The primary endpoints will be assessed by the following laboratory tests. The choice of laboratory assay may depend in part on how the 2019-2020 vaccine components and circulating strains affect which laboratory assay is most effective in assessing specific antigens.

- HI and/or MN responses to *egg*-grown vaccine reference viruses for all vaccine viruses for each study season at approximately 28 days, including the following endpoints
  - o Seroconversion rate (SCR) defined as the proportion of participants with paired samples that achieved ≥4-fold rises comparing post- versus pre-vaccination titers
  - Geometric mean titers (GMT) and the ratio of post-vaccination titers between the two vaccines (post-vaccination GMT ratio);
  - Geometric mean-fold rise (GMR) defined as the ratio of the post-vaccination titer
     value to the pre-vaccination value
  - o Elevated post-vaccination titers at thresholds greater than 1:40, 1:80, 1:160
- MN responses to the *cell*-grown influenza A/H3N2 (using MDCK-SIAT or other appropriate cell line) vaccine reference viruses at approximately 28 days postvaccination, including the following endpoints:
  - o SCR, post-vaccination GMT ratio, GMR, and elevated post-vaccination titers

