# 9.2 Statistical Analysis

HI and MN results will be measured by four primary parameters: SCR, post-vaccination GMT ratio, GMR, and post-vaccination titers equal or greater than seropositive thresholds at 1:40, 1:80, and 1:160. SCR will be defined as the proportion of participants with paired samples that achieved ≥ 4 fold rise comparing post vs pre-vaccination titers and post vaccination titers ≥ 1:40. GMR will be defined as the mean of the ratio of post-vaccination HI/MN titer and pre-vaccination HI/MN titer for each subject.

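### Between 30 and 54 comparisons are primary, each tested at 0.05, with no lead endpoint or multiplicity rule and with a primary list that differs between sections

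*Combined protocol and SAP*

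**What the plan says.** Section 9.2 opens with "HI and MN results will be measured by four primary parameters: SCR, post-vaccination GMT ratio, GMR, and post-vaccination titers" at or above three thresholds (1:40, 1:80, 1:160). Section 5.1 lists the same parameters, with "Elevated post-vaccination titers at thresholds greater than 1:40, 1:80, 1:160". It applies them to every egg-grown vaccine virus by either or both assays, and to cell-grown A/H3N2 by MN. The last paragraph of 9.2, which also covers the primary analyses, says "All tests will be 2-tailed with a level of significance of .05".

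The sections that define the primary set do not match:

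- **HI to egg-grown A/H3N2** is in the primary objective (4.1, "B/Yamagata, and B/Victoria, and egg-grown and cell-grown A/H3N2") and within the scope of 5.1, but 5.2 lists it as a secondary endpoint.
- **MN to the other subtypes and lineages** is within the scope of 5.1, but 4.2 makes it secondary.
- **HI to cell-grown A/H3N2** is in 4.1 but not in 5.1.

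Section 3.3 describes benefit "as measured primarily by humoral immune responses to MDCK cell-grown vaccine strains". Section 5.1 adds "The choice of laboratory assay may depend in part on how the 2019-2020 vaccine components and circulating strains affect" which assay works best, and 7.2 leaves the combination of assays and antigens open in the same way. Section 9.1 builds the sample size on SCR alone: "We intend to have the power to show a 30% relative increase in SCR in the RIV arm compared to the IIV arm".

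**The concern.** Section 3.1 states a single primary hypothesis, and 3.2 says studies of this kind will inform whether a preferential recommendation is warranted. The plan offers dozens of unadjusted tests of that hypothesis and never says which result decides it. The 0.05 level therefore belongs to each test and not to the primary conclusion, and the 80% power belongs to one SCR comparison that is not named as the lead. Because the sections disagree, two analysts following the plan could report different primary sets, and a reader could not tell which results had been primary from the start.

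**Working it through.** **1. The plan's own figure.** Section 9.1: two-sided 0.05, 80% power, SCR 40% against 40% × 1.30 = 52%, mean 46%. The pooled two-proportion formula gives, per arm,

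n = [1.96·√(2·0.46·0.54) + 0.8416·√(0.40·0.60 + 0.52·0.48)]² / 0.12² = (1.3815 + 0.5889)² / 0.0144 = 269.6, so 270, or 540 in total.

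This matches Table 2, and the same formula reproduces all 12 rows. The planned size is therefore that of one test at 0.05.

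**2. Count of primary tests.** SCR, GMT ratio and GMR plus three thresholds make 6 tests per assay/antigen set.

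- 5.1, one assay per egg-grown virus: 4 + 1 = 5 sets, 5 × 6 = 30.
- Honouring 4.2 and 5.2: HI for A/H1N1, B/Yamagata and B/Victoria, MN for egg-grown and cell-grown A/H3N2: again 5 sets, 30.
- 4.1: five HI and two MN sets, 7 × 6 = 42.
- 5.1, both assays for every egg-grown virus: 8 + 1 = 9 sets, 54.

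**3. Independence, as a reference.** In either direction the chance is 1 − 0.95^k: 78.5% (30), 88.4% (42), 93.7% (54). Each two-sided test favours RIV4 by chance with probability 0.025, so in that direction it is 1 − 0.975^k: 53.2%, 65.5%, 74.5%. Six tests on the same titres are not independent, so these overstate the error rate.

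**4. With correlation.** The documents give no correlation, so every value here is assumed. Pre- and post-vaccination log2 titres were simulated with no arm effect and 209 per arm, and all six tests were derived for each set.

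| Chance of at least one p < 0.05 | 30 tests | 42 tests | 54 tests |
|---|---|---|---|
| Either direction, between-virus correlation 0.2–0.5 | 56–65% | 64–76% | 72–84% |
| Favouring RIV4, same correlations | 30–37% | not run | 42–53% |

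At a between-virus correlation of 0.7 the either-direction figure is about 50–70% across the three counts. If every pair of tests is given the same correlation, 0.5 gives 51% (30) and 64% (54), and 0.9 gives 17% and 20%. All are well above 5%.

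SCR alone does not escape. Under independence, 1 − 0.95^5 = 22.6% for five sets and 1 − 0.95^9 = 37.0% for nine. The simulations came out close to these.

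**5. Power.** The minimum Group One target is 440 (6.3.2). Less 5% (9.1) this is 418, or 209 per arm if all are randomized 1:1. For 40% against 52%:

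- Single test at 0.05: (0.12·√209 − 1.3815)/0.6997 = 0.505, power 69%.
- First Holm step across four strains, 0.05/4 = 0.0125, z = 2.498: (1.7348 − 1.7605)/0.6997 = −0.037, power 49%.

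Bonferroni over the whole set would need 1,094 (30 tests) to 1,188 (54 tests) in total instead of 540.

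**The case against.** **The trial may be descriptive.** Immunogenicity studies commonly report each strain, 4.1 asks for a comparison, and nowhere does the plan say that one significant result proves the hypothesis. That stands: a reader might infer an any-one-wins success rule, and the documents contain none. What remains is that they contain no other rule either. Section 9.1 mentions regulatory criteria that use both GMR and SCR, but the plan adopts no margin and no requirement that all comparisons succeed.

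**54 is the widest count.** It requires both assays for all four egg-grown viruses, against the secondary listings in 4.2 and 5.2. That also stands, so 30 and 42 should be given beside it.

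**The error rate depends on assumptions.** A reader might quote one figure, or the 79–94% from independence, as a property of the plan. The documents support neither, since no correlation is given. The event that bears on the stated hypothesis is a false result favouring RIV4, which is less likely than a false result in either direction.

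**The open assay choice is not evidence of choosing on results.** Sections 5.1 and 7.2 tie it to vaccine components, circulating strains and assay performance. Study staff know the arms (6.1), but nothing says titres by arm will be available when assays are chosen. The steering committee reviews and confirms analysis plans (11.1), though no hierarchy or timing is set. The gap is that no time is given by which the choice is locked.

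**Conclusion.** The point holds in this form: 30 to 54 primary comparisons (42 by 4.1), each two-sided at 0.05, no lead endpoint or multiplicity rule, and a primary list that contradicts itself on three items. With no true difference, at least one nominally significant result favouring RIV4 would be expected roughly 30–37% (30 tests) to 42–53% (54 tests) of the time, and one in either direction roughly 55–65% to 70–85%. These rest on assumed between-virus correlations of about 0.2–0.5, and stronger correlation lowers them. That the rate is far above 5% did not depend on the structure tried.

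A reader might also infer that the documents already single out MN to cell-grown A/H3N2 as the lead. They do not: 3.3 refers to cell-grown strains in general, 7.2 ranks no antigen, and the SCR assumptions in 9.1 concern influenza A subtypes.

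**What to change.** - Name one primary parameter, antigen and assay, tested two-sided at 0.05. SCR is the natural parameter because 9.1 is built on it. MN to cell-grown A/H3N2 is one option consistent with 3.3, but the choice is the sponsor's.
- Use one SCR definition. The opening of 9.2 requires a four-fold rise and a post-vaccination titre of at least 1:40; its primary-objective paragraph, like 5.1, requires the rise alone.
- Make the other strains' SCR and GMT ratios secondary, in a fixed order or with Holm. Report GMR and the threshold comparisons with confidence intervals only.
- Fix the assay for each antigen, in a dated document, before any titre is linked to arm.
- Carry the same list through 4.1, 4.2, 5.1 and 5.2.

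This needs protocol and SAP wording only, with no added participants or samples. The single primary test is the one the sample size already assumes, so it loses no power to multiplicity. Its power is still about 69%, not 80%, at the minimum Group One target, and higher if more are enrolled (6.1 allows 550–700 in total). Making four strains co-primary with Holm instead would start at about 49%. The downside is that fewer results can be called primary.
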